#### **7.1.5 Pregnancies and Contraception Requirements for Females**

For the purposes of this study, a female of childbearing potential is defined as any female who has experienced menarche and is pre-menopausal. A postmenopausal state is defined as no menses for 12 months without an alternative medical cause in a previously menstruating female; in the absence of 12 months of amenorrhea, a single FSH measurement is not sufficient evidence of postmenopausal status.

For the purposes of this study, acceptable contraception is defined below based on Nonclinical Safety Studies for the Conduct of Human Clinical Trials and Marketing Authorization for Pharmaceuticals: ICH M3(R2) dated January 2010, and other available guidelines (“U.S. Medical Eligibility Criteria for Contraceptive Use, 2010” 2010; “Recommendations related to contraception and pregnancy testing in clinical trials” 2014; “M3(R2) Nonclinical Safety Studies for the Conduct of Human Clinical Trials and Marketing Authorization for Pharmaceuticals” 2010):

All female subjects of childbearing potential must use highly effective contraception, which includes the use of one or more of the following acceptable methods:

1. Surgical sterilization (e.g., bilateral tubal occlusion or ligation, hysterectomy, bilateral salpingectomy, bilateral oophorectomy)
2. Total (as opposed to periodic or cyclic) abstinence from heterosexual intercourse
3. Hormonal contraception associated with consistent inhibition of ovulation; these may include (but are not necessarily limited to) oral, intravaginal, implantable, injectable, or transdermal delivery methods.
  - a. Progesterone only oral contraceptives are excluded as a highly effective method, as they do not consistently inhibit ovulation.
4. Intrauterine device/systems
5. Exclusive monogamous heterosexual intercourse with a sterilized (i.e., vasectomized) or otherwise non-fertile (e.g., castrated) male partner

Any pregnancy occurring in a female subject or the female partner of a male subject, from the first study drug administration through the Follow-up visit must be reported within

24 hours of the investigator's awareness of the pregnancy. See *MTI-109 SAE Report Form and Pregnancy Report Form Completion Guidelines* for complete instructions.

The investigator will follow the pregnancy to delivery or other pregnancy outcome.

Pregnancy in a female clinical trial subject or female partner of a male clinical trial subject is not an SAE per se. Complications of such pregnancies (for example, spontaneous abortion) may qualify as SAEs and should be reported as such even if they occur after the Follow-up visit. Any congenital anomalies/birth defects must be recorded and reported as SAEs. See *MTI-109 SAE Report Form and Pregnancy Report Form Completion Guidelines* for complete instructions.

### **7.1.6 Worsening of Pruritus or Psoriasis**

Pruritus or psoriasis should be recorded as an AE or SAE only if considered by the investigator to have unexpectedly worsened in severity or worsened beyond the subject's normal fluctuations during the study. It is important to include a description of the nature of the unexpected worsening when recording the AE or SAE (e.g., new psoriasis lesions in previously uninvolved skin or pruritus requiring use of excluded therapy).

## **7.2 Methods and Timing for Recording and Reporting Adverse Events**

### **7.2.1 Adverse Event Reporting Period**

Any AE occurrence during the study must be recorded on source documentation and eCRF at the site, in accordance with protocol instructions.

AEs and SAEs will be recorded from the first study drug administration through the Follow-up visit. After the Follow-up visit, only SAEs that are believed to be drug-related should be reported.

After informed consent, but prior to initiation of study drug, only SAEs considered by the investigator to be caused by a protocol-mandated intervention will be collected (e.g., SAEs related to invasive procedures such as blood collection). These procedure-related SAEs should only be reported on the source documents and SAE form, not on the AE eCRF. Subjects who undergo screening procedures but are not randomized into the study will not have SAEs recorded in the clinical database.

### **7.2.2 Eliciting Adverse Events**

Investigators will seek information on AEs and SAEs at each subject contact through the Follow-up visit. All AEs and SAEs, whether reported by the subject or noted by authorized study personnel, will be recorded in the subject's medical record and on the AE eCRF page, and, if serious, on the SAE form. For each AE and SAE recorded, the investigator will make an assessment of seriousness, severity, and causality.

### 7.2.3 Assessment of Severity

All AEs entered into the eCRF will be graded for severity using the National Cancer Institute Common Terminology Criteria for Adverse Events (NCI CTCAE) v4.03 ([“Common Terminology Criteria for Adverse Events \(CTCAE\)” 2010](#)) to describe the maximum intensity of the adverse event.

If the AE cannot be found in the event-specific NCI CTCAE grading criteria, the investigator should use the definitions for Grade 1, 2, 3, and 4 in [Table 1](#).

**Table 1 Adverse Event Grading**

Grade	Severity	Alternate Description a
1	Mild (apply event-specific NCI CTCAE grading criteria)	Asymptomatic or mild symptoms; clinical or diagnostic observations only; intervention not indicated.
2	Moderate (apply event-specific NCI CTCAE grading criteria)	Minimal, local or noninvasive intervention indicated; limiting age-appropriate instrumental activities of daily living (ADL b )
3	Severe (apply event-specific NCI CTCAE grading criteria)	Severe or medically significant but not immediately life-threatening; hospitalization or prolongation of hospitalization indicated; disabling; limiting self care ADL c
4	Very severe, life threatening, or disabling (apply event-specific NCI CTCAE grading criteria)	Life-threatening consequences; urgent intervention indicated.
5	Death related to AE	

a Use these alternative definitions for Grade 1, 2, 3, and 4 events when the observed or reported AE is not in the NCI CTCAE listing. A semi-colon indicates ‘or’ within the alternate description of the grade.

b Instrumental ADL refer to preparing meals, shopping for groceries or clothes, using the telephone, managing money, etc.

c Self care ADL refer to bathing, dressing and undressing, feeding self, using the toilet, taking medications, and not bedridden.

Source: National Cancer Institute Common Terminology Criteria for Adverse Events (NCI CTCAE) v4.03 ([“Common Terminology Criteria for Adverse Events \(CTCAE\)” 2010](#))

Note that severity, a measure of intensity, is not equivalent to seriousness, a regulatory definition of outcome. Regardless of severity, some AEs may meet the criteria for seriousness. See [Section 7.1.2](#) for the definition of an SAE.

If an adverse event changes in severity during the same study period (e.g., treatment period), only the highest severity grade will be recorded on the eCRF.

### 7.2.4 Assessment of Causality

The investigator’s assessment of causality must be provided for all AEs (serious and non-serious). An investigator’s causality assessment is the determination of whether there exists a

reasonable possibility that the investigational product caused or contributed to an AE. Causality of an AE will be assessed by the investigator using the following terms:

- **Likely Related:** A reaction that follows a reasonable temporal sequence from administration of the study drug; that follows a known or expected response pattern to the suspected study drug; and for which other potential etiologies are considered less likely factors than the study drug.
- **Likely Unrelated:** A reaction that, considering all potential etiologies, is most likely due to factors other than the study drug.

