### **7.3 Follow-up of Adverse Events and Serious Adverse Events**

The investigator must make every effort to follow all AEs and SAEs regardless of attribution until judged resolved or stabilized, the subject is lost to follow-up, or it has been determined that study drug treatment or participation in the study is not the cause of the AE or SAE.

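### The two causality terms in Section 7.2.4 do not express the section's own reasonable-possibility standard, and some adverse events that meet the standard fit neither term

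*Protocol*

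**What the plan says.** Section 7.2.4 of the protocol contains both a standard and the terms for recording it.

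- **Standard.** The investigator decides whether there is a "reasonable possibility that the investigational product caused or contributed to an AE".
- **Likely Related.** Three limbs are joined by an explicit *and*. The first is reasonable timing. The other two ask for a reaction "that follows a known or expected response pattern to the suspected study drug; and for which other potential etiologies are considered less likely", with the drug as the comparator.
- **Likely Unrelated.** This term has a single condition, worded as follows: "A reaction that, considering all potential etiologies, is most likely due to factors other than the study drug".

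The section directs the investigator to use these terms and gives no third term or default. The assessment is compulsory: under 7.2.2, for each event recorded, "the investigator will make an assessment of seriousness, severity, and causality", and 7.2.4 repeats the requirement for serious and non-serious events alike.

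The exact term *likely related* is used in two other places: the sentence in 7.4 on serious events learned of after a participant has left the study, and one discontinuation criterion in 5.6. Section 8.11.1 tabulates treatment-related events by arm without defining them separately.

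**The concern.** The standard asks only whether the drug could reasonably have played a part. It does not require a recognised pattern, and it does not require the drug to be the leading cause. *Likely Related* requires both. *Likely Unrelated* requires that something else be the leading cause. Between the two lie events that satisfy the standard and have no term, although a term must be entered for each of them.

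What is at stake is the meaning of the related label. A count of related events from this trial would rest on how each site resolved a question that the protocol leaves open, and two sites could record the same event differently. Safety and tolerability is a secondary objective (Section 2), and the related table is one of its standard displays. The label also decides whether the investigator is told to report a serious event learned of after discharge, and it triggers one criterion in 5.6.

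**Working it through.** No arithmetic applies. The check compares the standard and the two terms as worded, one type of event at a time. Timing is taken as fitting throughout, because timing is not in dispute.

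1. **Known pattern, other causes less likely than the drug.** Meets the standard. Meets all three limbs of *Likely Related*. No problem.
2. **New kind of reaction, other causes less likely than the drug.** Meets the standard: the timing fits and nothing explains the event better. Fails *Likely Related* on the pattern limb. Fails *Likely Unrelated* because other factors are not the most likely cause. Fits neither term.
3. **Drug and other causes equally likely, pattern known or not.** Meets the standard: an even chance is a reasonable possibility. Fails *Likely Related* on the third limb, since the other causes are not less likely. Fails *Likely Unrelated*, since they are not the most likely. Fits neither term.
4. **Another cause more likely, but the drug may have contributed.** Meets the standard, which accepts contribution. Recorded as *Likely Unrelated*. A term exists, but it gives the opposite answer to the standard.
5. **Another cause more likely and no reasonable possibility of a drug role.** Does not meet the standard. Recorded as *Likely Unrelated*. No problem.

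Types 2 and 3 have no term. Type 4 has a term that disagrees with the standard. These are types of case; nothing in the protocol says how often each would occur.

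Two readings that might rescue the wording were tried.

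- **Semi-colon as *or*.** Footnote a to Table 1 says that a semi-colon means *or*, but it confines this to use "within the alternate description of the grade". It concerns severity grading, and 7.2.4 joins its limbs with *and*.
- **A broad sense of known or expected.** The phrase is not defined. If it covers any pharmacologically plausible effect, type 2 shrinks. Types 3 and 4 remain, because they turn on the third limb and on *Likely Unrelated*, not on the pattern.

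Uses of the label:

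- **8.11.1.** The treatment-related table is affected, on the assumption that it is built from the 7.2.4 term. The protocol offers no other source.
- **7.4.** Prompt reporting of a serious event learned of after discharge depends on *likely related*.
- **5.6.** One criterion depends on an event being assessed as *likely related*.

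**The case against.** The strongest answer is that the opening sentence governs. It says what the assessment is, and the two terms only record the result. An investigator who finds a reasonable possibility would then choose *Likely Related* and treat the rest as guidance. That is a sensible way to use the form, and it makes this a fault of drafting rather than an assessment that cannot be completed. But the protocol does not say that the sentence prevails over the definitions. It directs that causality be assessed with the terms, and an investigator who follows them literally reaches a different answer for type 4 and none for types 2 and 3.

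The second answer is that little depends on the label, and much of this stands.

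- In-study serious events go to the Sponsor within 24 hours whatever their cause (7.4).
- Investigators "must make every effort to follow all AEs and SAEs regardless of attribution", although 7.3 lets follow-up end once the drug or participation is found not to be the cause.
- All adverse events are tabulated by arm (8.11.1).
- Section 5.6 has further grounds, resting on the subject's safety or best interest in the investigator's or Sponsor's opinion, that need no causality label.
- The assessors are blinded (5.8.2), so the same wording applies in both arms.
- The separate SAE and pregnancy form guidelines named in 7.4 are not shown and may settle the choice for serious events.

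Three stronger conclusions that a reader might draw are not supported.

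- **That new toxicities would be under-reported.** The protocol does not say which term a site would choose for an event that fits neither, so the direction is unknown, and in-study serious events are notified regardless.
- **That expedited reporting of unexpected events is blocked, because an unexpected event can have no expected pattern.** Section 7.5 gives that duty to the Sponsor or its designee and does not say that its judgment of relatedness is bound by the investigator's term.
- **That the relatedness wording conflicts across the protocol.** Sections 7.2.1, 7.5 and 8.11.1 use ordinary phrases for relatedness, and no contradiction among them is shown.

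**Conclusion.** The point holds as a conflict within Section 7.2.4. The two permitted terms do not implement the stated standard, they leave two types of event without a term, and they allow an event to which the drug may have contributed to be recorded as *Likely Unrelated*.

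Its size cannot be determined: the protocol gives neither the frequency of such events nor a rule for choosing a term, so no shift in the related count can be stated in either direction or in either arm. The reach is limited to the related label and its uses in 8.11.1, in the post-discharge sentence of 7.4 and in one criterion of 5.6. The efficacy endpoints do not use it.

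The conclusion assumes that the definitions are applied as written, that the treatment-related table uses the 7.2.4 term, and that the unseen guidelines do not already resolve the choice. If those guidelines do resolve it for serious events, the point would still stand for non-serious events unless they cover those too. The wording should be corrected, because the protocol states a rule that conflicts with its own standard and the correction is small.

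**What to change.** Reword the two terms in 7.2.4 so that they give a yes/no answer to the section's own reasonable-possibility question and so that every adverse event falls under exactly one of them. Timing, pattern and competing causes can stay as considerations that inform the answer, rather than as conditions that must all be met.

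Then reconcile the uses of *likely related* in 7.4 and 5.6 with the reworded terms. For 5.6, the sponsor must settle what the term means there when the definition changes. No discontinuation rule or other clinical rule is proposed here.

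The cost is a short wording change and matching guidance for the eCRF and the SAE form. The number of events labelled related may change by an unknown amount.

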### **7.3 Follow-up of Adverse Events and Serious Adverse Events**

The investigator must make every effort to follow all AEs and SAEs regardless of attribution until judged resolved or stabilized, the subject is lost to follow-up, or it has been determined that study drug treatment or participation in the study is not the cause of the AE or SAE.

### **7.4 Reporting Serious Adverse Events to the Sponsor and Institutional Review Board (IRB) or Ethics Committee (EC)**

The Sponsor or designee is under obligation to report certain SAEs to regulatory authorities related to investigational drugs in clinical trials. The Sponsor or designee must be notified within 24 hours of an AE when the investigator determines that an AE meets the protocol definition of an SAE, regardless of the cause or relationship to study drug.

An SAE related to study participation occurring before study drug administration and after informed consent should be promptly reported to the Sponsor. If the investigator learns of any SAE at any time after a participant has been discharged from the study, and the SAE is considered likely related to study drug, the SAE should be promptly reported to the Sponsor.

Please see the *MTI-109 SAE Report Form and Pregnancy Report Form Completion Guidelines* for safety reporting instructions.

The investigator must also comply with applicable requirements concerning reporting of SAEs to the Institutional Review Board (IRB) or Ethics Committee. This may include initial or follow-up notification of an SAE or other safety information.

### **7.5 Reporting Serious Adverse Events to Regulatory Authorities and Study Investigators**

The Sponsor, or its designee, is responsible for submitting reports of serious, unexpected related adverse events to regulatory authorities on an expedited basis, according to the ICH E2A Guideline and to other regulatory authorities according to national and local regulations as required. The Sponsor, or its designee, is responsible for prompt submission to the IRB or EC of any expedited SAE reports submitted to regulatory authorities. All investigators participating in ongoing clinical studies with serlopitant will receive copies of the SAE reports submitted on an expedited basis to regulatory authorities.

## 7.6 Emergency Unblinding

The investigator will immediately notify the Sponsor or the medical monitor to discuss the need for unblinding any subject via IWRS. There is no specific antidote for serlopitant and usual supportive medical management is recommended in the case of a medical emergency.

## 8 STATISTICAL METHODS

All statistical processing will be performed using SAS® unless otherwise stated. No interim analyses are planned. Endpoints will be summarized with descriptive statistics by treatment group and visit. For continuous variables, the following information will be presented: n, mean, standard deviation, median, minimum and maximum. For categorical variables counts and percentages will be used.

The primary method of handling missing efficacy data will be the method of Markov Chain Monte Carlo (MCMC) multiple imputation. As one sensitivity analysis, the last observation carried forward method (LOCF) will be used (i.e., the last available on-therapy observation for a subject will be used to estimate subsequent missing data points). As a second sensitivity analysis, a repeated measures model will be used on observed data.

Baseline for measures other than the eDiary and actigraphy daily measures, will be the last recorded value prior to the start of treatment. For daily measures including the WI-NRS, baseline will be the average result measured over the week prior to treatment. Additionally, the daily measures will be summarized at Weeks 2, 4, 6 and 8 by averaging the daily results associated with these weeks.

A statistical analysis plan (SAP), describing all statistical analyses will be provided as a separate document. The SAP will be finalized prior to unblinding of the study treatments.

### 8.1 Decision Rule and Sample Size

The decision rule is based on the Phase 2b screening methodology presented in Fleming and Richardson ([Fleming 2004](#)). The two-category decision guideline as applied to this clinical trial compares the observed one-sided p-value for the primary endpoint to two categories: (0.025, 0.05) and (0, 0.025).

- If the one-sided p-value is between 2.5% and 5% then the serlopitant-based regimen is plausibly efficacious and should be evaluated definitively in a subsequent Phase 3 clinical trial.
- If the one-sided p-value is less than 2.5%, then the serlopitant-based regimen will have met the generally accepted level of evidence required to demonstrate efficacy.

The sample size of 100 per group has been selected to achieve 90% power for the primary endpoint with

- 5% one-sided alpha and responder rates of 24% (placebo) and 43.5% (serlopitant)
- 2.5% one-sided alpha and responder rates of 24% (placebo) and 46% (serlopitant)

Testing of the key secondary endpoints will take place should statistical significance be reached for the primary endpoint. Testing within the key secondary endpoints will be hierarchical with testing starting with the WI-NRS Week 4 responder rate, then the Day 7 WI-NRS endpoint, and finally the Day 3 WI-NRS endpoint.

The sample size calculations have been performed in PASS 13 ([“PASS 13 Power Analysis and Sample Size Software” 2014](#)) and use a Chi-Squared test. The primary analysis will control for the stratification factors. It is expected that this unstratified power estimate will under-estimate the true power as it does not take the variance reduction resulting from stratification into account ([Matts 1988](#)).

## **8.2 Handling of Missing Data and Excluded Therapy Use**

Should a determination of treatment period (on treatment, pre-treatment) be required for adverse events or concomitant medication but the corresponding date is missing, or is a partial date, the event/medication will be considered on treatment unless the portions of the date that are available indicate this is not possible.

The primary method of handling missing efficacy data will be MCMC multiple imputation. Imputation will be conducted within each treatment group independently, so the pattern of missing observations in one treatment group cannot influence missing value estimations in another. For each imputation process, 25 imputations will be performed.

If a subject fails to complete their eDiary for a week or more the primary endpoint (WI-NRS), may be missing. If the Week 8 measure from the eDiary is unavailable because the subject withdrew from the study due to lack of efficacy, or the subject uses an excluded therapy to treat psoriasis or pruritus, their responder status will be defined as non-responder. If the Week 8 value is missing for any other reason, the WI-NRS change from baseline value will be based on imputed data. Missing Week 8 WI-NRS values from which the 4-point responder status is derived will be estimated by MCMC.

Missing WI-NRS data will be derived for the analysis using the method of MCMC multiple imputation. Since both primary and key secondary endpoints require WI-NRS, the following steps will be followed:

1. Using the daily eDiary data, calculate Baseline and Week 2 through Week 8 values by averaging available values. If any values are available, these will be used i.e. a minimum of 1 observation is required to compute a week's average.
2. From step 1, create a dataset for each treatment group, of subjects with observed values and those needing estimation by MCMC. The missing WI-NRS values in each dataset will be filled in using the MCMC method to generate 25 datasets.

The resulting datasets for each treatment arm will be combined into one complete dataset.

Syntax:

```
proc mi data=datain out=dataout seed=&seed. Nimpute=25 <options>;  
  where trtpn=(TRT); /* Note TRT = [1, 2]; depending on treatment group */;  
  mcmc chain=single;  
  var baseline d2 d3 d4 d5 d6 d7 week2 week3 week4 week5 week6 week7 week8;  
run;
```

3. From each complete dataset, the dichotomous responder rate will be determined.

Each complete dataset formed by multiply imputed data will be analyzed as specified for the particular analysis. The results from the analyses will be combined into a single inference using SAS® PROC MIANALYZE. In the case of the primary analysis and the secondary responder analyses, the Cochran Mantel Haenszel (CMH) statistics computed in the analyses of WI-NRS responder rates will be normalized using the Wilson-Hilferty transformation prior to combining them using SAS® PROC MIANALYZE

A total of 2 random seeds will be needed to impute missing data. Those random seeds have been pre-specified by using a random number generator:

- WI-NRS Serlopitant: Seed= 85162995
- WI-NRS Placebo: Seed= 878201528

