## **5.6 Study Drug Discontinuation**

Subjects should be discontinued from study drug treatment in the following situations:

- A female subject becomes pregnant
- The subject decides to discontinue study drug treatment, or withdraw consent from the study
- The subject receives a strong CYP3A4 inhibitor
- The subject receives an excluded medication for treatment of pruritus or psoriasis
- Any medical condition that may jeopardize the subject's safety if study drug is continued, in the investigator's and/or Sponsor's opinion
- Discontinuation is deemed to be in the best interest of the subject, in the investigator's and/or Sponsor's opinion
- The subject experiences a NCI CTCAE Grade 3 or higher treatment emergent AE that is assessed as likely related to study drug

The Sponsor or designee should be contacted within 24 hours of investigator's awareness of any study drug treatment discontinuation. Investigators should make every effort to contact the Sponsor or designee before discontinuing study drug treatment, if possible.

Subjects who discontinue treatment with study drug prior to completing the treatment period will have a Follow-up visit 14 days after their last dose of study drug (see [Section 6.5.9](#)). Every effort should be made for subjects to complete the Follow-up visit after a subject has discontinued from study drug.

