## **6.6 Early Termination**

Early termination of a subject from the study may occur due to the following reasons:

- lost to follow-up
- withdrawal of consent by the subject

In accordance with legal requirements and International Conference on Harmonisation (ICH) – Good Clinical Practice (GCP) guidelines, every subject or his/her legal representative has the right to withdraw from the study at any time and without providing reasons. If a subject is willing to provide a reason for withdrawal, this will be recorded in the electronic Case Report Form (eCRF). The Investigator or site staff must make every effort to contact subjects who are suspected of being lost to follow-up. A minimum of two attempted telephone contacts and a certified letter are required before a subject can be deemed as lost to follow-up. Attempts to contact such subjects must be documented in the subject's source documents.

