#### **8.4 Subject Disposition**

An accounting of all randomized subjects by disposition will be presented. Subjects who discontinue study drug prematurely or withdraw from the study will be summarized and listed, with a description of the reason for early termination/withdrawal.

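### Section 8.2 counts lack of efficacy as non-response only after withdrawal from the study, so a subject who stops study drug early for lack of efficacy is imputed and can count as a responder

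*Protocol*

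**What the plan says.** Section 8.2 names two routes from a missing Week 8 WI-NRS to non-response. One is that the value is "unavailable because the subject withdrew from the study due to lack of efficacy". The other is use of an excluded therapy for psoriasis or pruritus. Everything else goes to multiple imputation: "If the Week 8 value is missing for any other reason, the WI-NRS change from baseline value will be based on imputed data". Imputation is run within each arm from baseline, Days 2-7 and Weeks 2-8. No variable records that drug was stopped, or why. For a weekly average, "a minimum of 1 observation is required to compute" it.

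Other sections keep stopping drug and leaving the study apart:

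- Section 5.6 lists them as alternatives: "The subject decides to discontinue study drug treatment, or withdraw consent from the study". It then sets the path for those who stop drug: "Subjects who discontinue treatment with study drug prior to completing the treatment period will have a Follow-up visit 14 days after their last dose".
- Section 6.6 covers study exit only ("Early termination of a subject from the study may occur due to the following reasons") and gives two reasons, loss to follow-up and withdrawal of consent. A subject need not give a reason for withdrawing.
- Section 8.4 joins the two events with an or: "Subjects who discontinue study drug prematurely or withdraw from the study will be summarized and listed", "with a description of the reason for early termination/withdrawal".
- Section 8.3 names, as a group kept in the per-protocol population, subjects who come off study drug because of a documented lack of effect.

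Section 6.5.9 and Table 3 end the diary at Follow-up, 14 (+3) days after the last dose for an early stopper. The responder definition in 8.8 adds only the excluded-medication condition.

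**The concern.** The protocol has already chosen to count lack of efficacy as failure when Week 8 is missing. As worded, that choice reaches only a subject who withdraws consent with lack of efficacy recorded as the reason. A subject who stops drug for the same reason early in treatment and takes no excluded therapy falls under the any-other-reason clause, although 8.3 shows that the protocol foresees this group. Such a subject can be imputed as a responder on the primary endpoint. Two subjects with the same clinical event can therefore be classified differently because of how their exit is labelled.

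**Working it through.** **The plan's own figure.** Inputs from 8.1: 100 per group, 24% on placebo, 43.5% or 46% on serlopitant. For the pooled chi-squared test, power = Φ{[√n·(p2−p1) − z·√(2p̄(1−p̄))] / √(p1(1−p1)+p2(1−p2))}.

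- One-sided 5%, 43.5%: (1.95 − 1.645×0.6687)/0.6544 = 1.299, power 90.3%.
- One-sided 2.5%, 46%: (2.20 − 1.960×0.6745)/0.6564 = 1.338, power 90.9%.

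The stated 90% reproduces.

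**Who has no Week 8 entry.** Take Baseline as Day 1 and Week 8 as Days 50-56 (assumption). A last dose on Day S puts Follow-up, and the end of the diary, on Day S+14 to S+17. One entry is enough for a weekly value, so none exists if S+14 ≤ 49 (S ≤ 35) or, with the full window, S+17 ≤ 49 (S ≤ 32). A subject lost before Follow-up stops supplying entries sooner.

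**How 8.2 classifies a subject with Week 8 missing and no excluded therapy.**

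| Event | Result under 8.2 as written |
|---|---|
| Withdraws consent, lack of efficacy recorded | Non-responder |
| Stops drug for lack of efficacy, completes Follow-up | Imputed |
| Stops drug for lack of efficacy, later lost to follow-up | Imputed |

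**Size.** Let f be the share of an arm in the second and third rows, and p the probability that such a subject is imputed as a responder. The literal rule raises the arm's responder rate by f×p compared with counting them as failures, so the treatment difference moves by f_S×p_S − f_P×p_P. The protocol gives neither f nor p.

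For p, an illustrative model with 24 scenarios was used. Weekly improvement is normal with SD 2.5, autoregressive, with Week 4-8 correlation 0.5, 0.6 or 0.7. The mean either rises linearly to Week 8 or plateaus at Week 4. Subjects stop at Week 2, 3, 4 or 5 if improvement is under 1 point. Scores after stopping follow the on-drug course. At 24% and 43.5%, p is about 1-16% on placebo and 3-33% on serlopitant.

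| f serlopitant / f placebo (assumed) | Shift in treatment difference, percentage points |
|---|---|
| 1% / 1% | +0.01 to +0.17 |
| 2% / 2% | +0.03 to +0.33 |
| 5% / 5% | +0.06 to +0.83 |
| 2% / 5% | −0.15 to +0.01 |
| 1% / 5% | −0.48 to −0.05 |

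The top value is 5×(0.326 − 0.160) = 0.83. The ends of these ranges carry simulation error of a few hundredths of a point. If improvement is still under 1 point two weeks after stopping, p falls to 0.02-10% on placebo and 0.05-22% on serlopitant, and the maximum at 5% per arm is about 0.6 points.

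**Is 5% plausible?** With last-dose days uniform over Days 1-55 (assumption), 35/55 = 64% or 32/55 = 58% of stoppers who attend Follow-up lack a Week 8 entry. Reaching f = 5% through them needs 5/0.636 = 7.9% to 5/0.582 = 8.6% of an arm to stop for lack of efficacy without excluded therapy. So 5% is an upper-end assumption.

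**The case against.** The best case for the plan is that the wording is loose and the consequence negligible. Withdrawal may have been meant to include stopping drug: 8.4 plans a single reason field for both, and 8.3 groups drug discontinuation for lack of effect with non-responder criteria. The SAP, which is not shown, could clarify it. Imputing a subject who has supplied another 14-17 days of diary data is a defensible missing-at-random choice, and on-therapy LOCF, which would usually class these subjects as non-responders, is already planned. The group is narrow, because many early stoppers would take something on the broad excluded list and so already be non-responders.

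The points on size stand. The point on intent does not settle the matter: 5.6, 6.6 and 8.4 consistently separate the two events, and 8.2 fixes the rule, the code and the seeds in the protocol itself. LOCF is only a sensitivity analysis. If imputation is intended, the protocol should say so and explain why a recorded study withdrawal for the same reason is treated differently.

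Three stronger readings are tempting but unsupported:

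- **Attending Follow-up decides responder status.** It does not; a stopper later lost to follow-up is imputed too.
- **The protocol expressly imputes adverse-event stoppers.** Section 8.2 does not mention them; they fall under any other reason and are outside this point.
- **The rule favours serlopitant.** The shift is positive with equal shares, but it can be negative when more placebo subjects stop.

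**Conclusion.** The point holds on the literal text. A stated rule leaves out subjects whom the plan otherwise means to count as failures, namely those who stop drug for lack of efficacy by about Day 32-35, have no Week 8 entry and used no excluded therapy. Severity is minor. The effect on the treatment difference is below about 1 percentage point at assumed shares of up to 5% per arm, and smaller if the diary after stopping still shows no improvement. That size rests wholly on assumed values for f, the SD, the correlations, the stopping threshold and the Week 8 window. Confidence is high for the wording only, not for any effect on the trial's result.

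**What to change.** In the 8.2 clause, insert *discontinued study drug, or* before the reference to withdrawing from the study, so that a Week 8 value missing through either event for lack of efficacy is a non-response. Use the same term for this group in 8.2 and 8.3. State the rule for the Week 4 responder endpoint as well. With Week 4 as Days 22-28 it reaches only last doses by Day 4-7, so this is mainly for consistency. Observed Week 8 values are kept as now, which means a later stopper with a Week 8 entry is still judged on that entry.

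No new data are needed, since 8.4 already plans to report the reasons. The change should be made before unblinding. The cost is slightly lower responder rates and, with equal shares in both arms, slightly lower power. At one-sided 5%, power goes from 90.3% to 90.0-90.3% (f = 1%), 89.6-90.3% (2%) or 88.4-90.2% (5%). At one-sided 2.5%, it goes from 90.9% to 88.9-90.8% (5%).
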